13.4.3 Supportive Analyses of the Primary Endpoint(s)/Outcome(s)

If any relevant covariates are imbalanced between arms A and C, the primary comparison will also be performed using a multivariable logistic regression model controlling for those variables.

The primary comparison will be repeated between arms A and B, using the binomial test of proportions with two-sided alpha level of 0.05.

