All arms will undergo an Initial Dose Escalation (IDE) Day and updosing regimen with a maintenance phase of OIT or placebo to a maximum of 4,000 mg protein daily, as peanut flour, in the OIT groups, and to a maximum of an equivalent amount of oat flour for the placebo group). (Part III, Figure 1). After maintenance is achieved, all subjects will begin performing DBPCFCs (staged so as to ensure safety) at Week 104 and every 13 weeks thereafter (Part IV, Figure 1). At Week 104, individuals that reach criteria (Part IV, Figure 1) will, based on the randomization that was done at the start of the study, either stop therapy with peanut and be switched to oat flour, or will be maintained on 300 mg peanut protein per day (Parts V, Figure 1). If subjects fail the week 104 DBPCFC they will not be given home doses. Those that fail the week 104 FC will remain in the study and return for a study completion visit at week 117 to meet the primary endpoint (will be analyzed in the intent to treat comparisons). All subjects will be evaluated every 13 weeks thereafter until the end of study.

Individuals in Arm A will be defined as "clinically tolerant" if there is no clinical reactivity at the Week 104 and Week 117 (or equivalent) DBPCFC. Clinical reactivity is defined as any objective reaction based on the Bock's Criteria (**Appendix 4**). Individuals in Arm A who meet the definition of "clinically tolerant" will continue to avoid peanut protein (i.e. continue on 600 mg per day of oat flour) as long as each subsequent DBPCFC (performed every 13 weeks until end of study) shows no clinical reactivity.

Individuals in Arm B will be defined as "desensitized" to a minimum of 300 mg per day of peanut protein if they show no clinical reactivity at DBPCFCs (week 117 (or equivalent) to end of study).

Individuals in Arm C will be defined as "natural loss of responsiveness" if they show no clinical reactivity at DBPCFCs (week 117 (or equivalent) to end of study).

We plan to identify the basic immune mechanisms which can explain the differences in the effects of OIT in individuals who do or do not become clinically tolerant and to determine whether immune monitoring can predict the safety and efficacy outcomes in peanut OIT protocols. After initial screening and enrollment, there are three phases of the study:

- Dose escalation and Build up Phase (Part III, Figure 1)
- Maintenance phase (Part IV, Figure 1)
- Tolerance and Desensitization Testing phase (Part V, Figure 1)

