13.1 Overview

This double blind, randomized, placebo controlled study in peanut-allergic children and adults intends to identify basic immune mechanisms that explain the effects of OIT in individuals who do or do not become clinically tolerant and to determine whether immune monitoring can predict safety and outcomes in OIT protocols.

The 120 enrolled subjects will be randomized 2.4:1.4:1. Thus, there will be three arms: (1) Arm A (60 subjects) on peanut OIT until week 104 and once meeting criteria [*i.e.* 1) assigned to OIT treatment for minimum 104 weeks, 2) reaching maintenance 13 weeks prior to DBPCFC at week 104 3) no severe reactions (Grade 3, APPENDIX 4) to home dosing from Week 92-Week 104, and/or 4) no objective reactions, (Appendix 4) at the Week 104 DBPCFC] has been assigned to avoid peanut (i.e. 600 mg oat flour). (2) Arm B (35 subjects) on peanut OIT until week 104 and once meeting criteria, has been assigned to be maintained on 300 mg peanut protein (i.e. 600 mg peanut flour). (3) Arm C (25 subjects) that is maintained on placebo (oat flour) and once meeting criteria, will receive 600 mg oat flour beginning on week 104. This will be true even if a subject in the placebo group meets criteria at week 104. This way all participants will receive approximately the same volume of flour so that the subject blinding will be easier to maintain. The decision to maintain subjects on only 300 mg peanut protein after week 104 is for ease of eating peanut for so long. This upfront randomization is performed because our statistical analysis plan is focused on intent-to-treat principles.

The primary analysis is an intent-to-treat comparison of success rates between arms A and C, where success is defined by reaching and passing the DBPCFC at both 104 weeks and 117 (or equivalent) weeks.

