13.4. Analysis Plan

13.4.1 Analysis Populations

- Intent-to-treat (ITT) sample: All subjects who are randomized will comprise the ITT sample.
- Safety sample: All enrolled subjects who receive at least one dose of OIT or placebo. Participants in the safety sample will be analyzed according to the treatment they actually received, regardless of their randomized assignment.

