13.4.2 Primary Analysis of Primary Endpoint(s)/Outcome(s)

The primary analysis is an ITT comparison of success rates between arms A and C (defined in Section 13.1), where success is defined by reaching and passing the DBPCFC at Week 117 (or equivalent). An unevaluable test will be considered a failure. The analysis will be performed using the binomial test of proportions. A two-sided alpha level of 0.05 will be used. The success rate in each of the three arms will also be estimated, with 95% exact binomial confidence interval.

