13.6. Statistical Hypotheses

For the primary comparison, the following will be tested:

- Null hypothesis: The success rate (where success is passing the DBPCFC at both 104 and 117 (or equivalent) weeks) is equal in arms A (active treatment followed by 3 months of avoidance) and C (placebo).
- Alternative hypothesis: The success rate differs between arms A and C.

As a secondary comparison, the following will be tested:

- Null hypothesis: The success rate is equal in arms A and B (active treatment followed by 3 months of 300mg peanut protein treatment).
- Alternative hypothesis: The success rate differs between arms A and B.

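### The A-versus-B test on all randomised subjects is valid, but failures before the Week 104 switch dilute it; add a comparison stratified by the Week 104 challenge result

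*Protocol*

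**What the plan says.** Section 13.4.2 sets the primary analysis: "The primary analysis is an ITT comparison of success rates between arms A and C". Section 13.4.1 defines the population: "All subjects who are randomized will comprise the ITT sample". Section 13.4.3 then extends this to the two active arms: "The primary comparison will be repeated between arms A and B, using the binomial test of proportions with two-sided alpha level of 0.05". Section 13.6 gives the comparison its own null hypothesis: "Null hypothesis: The success rate is equal in arms A and B (active treatment followed by 3 months of 300mg peanut protein treatment".

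Sections 13.1 and 13.6 define success as passing the food challenge at both Week 104 and Week 117. Section 13.7 counts drop-outs as failures.

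The two arms have the same description up to the switch: "1) Arm A (60 subjects) on peanut OIT until week 104 and once meeting criteria" and "2) Arm B (35 subjects) on peanut OIT until week 104 and once meeting criteria". Section 3.1 says that subjects who meet the Week 104 criteria then, "based on the randomization that was done at the start of the study, either stop therapy with peanut and be switched to oat flour", or stay on 300 mg. Subjects who fail the Week 104 challenge get no further home doses. The same section gives testing whether a lower amount can maintain desensitisation as one reason for the 300 mg regimen.

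The analysis set was chosen deliberately. Section 13.1 states: "This upfront randomization is performed because our statistical analysis plan is focused on intent-to-treat principles".

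**The concern.** Up to Week 104, assignment to A or B changes nothing that a subject receives, and the study is double-blind. While the blind holds, assignment cannot influence who passes the Week 104 challenge. For A versus B, that result therefore behaves like a baseline variable.

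The planned test still places every earlier failure in both arms, at the same expected rate. A subject who never reaches the switch cannot show whether stopping differs from 300 mg. These subjects shrink the observed difference and add noise.

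Section 13.6 names A versus B as the secondary hypothesis, and it is the only A-versus-B test whose method the protocol sets out. At stake is whether a real difference after the switch is missed in data that could have shown it.

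**Working it through.** **Inputs.** From the protocol: 60, 35 and 25 subjects in A, B and C (13.1); Arm A success 0.35 among all randomised and Arm C 0.05 (13.7); two-sided alpha 0.05 (13.4.2, 13.4.3). Assumed, because the protocol gives neither: *s*, the share passing Week 104 (equal in A and B), and *b*, Arm B's Week 117 pass rate among those who passed Week 104. Success means passing at both visits.

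**Formula.** Power = Φ((d − 1.96·SE₀)/SE₁), where d is the difference in rates, SE₀ the pooled and SE₁ the unpooled standard error.

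**Plan's own figure (A v C).** Pooled rate (60×0.35 + 25×0.05)/85 = 0.262; SE₀ = 0.1046; SE₁ = 0.0754. (0.30 − 0.2051)/0.0754 = 1.26, so power is 89.6%. The stated 90% is reproduced.

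**A v B, one case (s = 0.7, b = 0.85).**
- As planned: 0.35 v 0.7×0.85 = 0.595, so d = 0.245. SE₀ = 0.1056, SE₁ = 0.1033. (0.245 − 0.2069)/0.1033 = 0.37, power 64%.
- Among those who passed Week 104: 0.35/0.7 = 0.50 v 0.85, so d = 0.35, with expected numbers 42 and 24.5. SE₀ = 0.1228, SE₁ = 0.1056. (0.35 − 0.2407)/0.1056 = 1.03, power 85%.

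The planned difference is *s* times the difference among passers: 0.7 × 0.35 = 0.245.

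**Range.** Exact enumeration of the pooled z-test, with the numbers passing Week 104 drawn as binomial(60, s) and binomial(35, s). Power as planned → among passers, Arm A fixed at 0.35 overall:

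| s | b = 0.70 | b = 0.80 | b = 0.85 | b = 0.90 |
|---|---|---|---|---|
| 0.6 | 11→14% | 25→39% | 34→57% | 45→76% |
| 0.7 | 28→36% | 52→70% | 65→85% | 76→95% |
| 0.8 | 52→61% | 79→90% | 89→97% | 95→99% |
| 0.9 | 76→81% | 95→97% | 98→99% | 99.6→99.9% |

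**Type I error.** With equal rates the planned test rejects in 5.2% of trials and the comparison among passers in 5.1 to 5.2% (s = 0.6 to 0.8). The gain is not bought with false positives.

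**Sensitivity.** Section 1.1 reports 6 of 16 tested subjects tolerant after avoidance (0.375). Using that as Arm A's rate among passers:

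| s | b = 0.70 | b = 0.85 |
|---|---|---|
| 0.6 | 53→67% | 82→96% |
| 0.7 | 62→74% | 90→98% |
| 0.8 | 71→80% | 96→99% |

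The loss is about 3 to 15 points here. At s = 0.6 it peaks near 16, with b of 0.75 to 0.80.

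**The case against.** A reader might infer that the planned test is wrong, or that 20 to 30 points of power are given away for nothing. The documents support neither reading.

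- **Validity.** The intent-to-treat test holds its error rate. It estimates the difference between two whole strategies (immunotherapy then stopping, or immunotherapy then 300 mg). It needs neither an intact blind nor a clear Week 104 rule, and Section 13.1 shows that it was chosen on purpose. That stands, and it is why the test should be kept.
- **Size.** The large losses rest on rates the protocol does not give. If 0.35 overall and 6/16 among passers are taken together, s = 0.35/0.375 = 0.93, where the loss is small. The two figures come from different studies, so this is only indicative. Section 8.3 expects all active subjects to reach 4,000 mg, but that concerns dose, not passing the challenge.
- **Standing.** A versus B is supportive in 13.4.3 and secondary in 13.6, and the sample size rests on A versus C. Section 13.4.4 also reports failure proportions for A and B separately with exact intervals. This limits the consequence but does not remove the dilution.
- **Definition.** Passing the Week 104 challenge and meeting the Week 104 criteria are different sets, because the criteria add three further conditions joined by an and/or. Section 13.4.2 also defines success by Week 117 alone, and Section 3.1 brings Week 104 failures back at Week 117. Under that definition a Week 104 failure is not automatically a failure.
- **Randomisation.** Section 8.3 says that subjects who met the criteria are randomised 1:1 at that point. Read literally, A versus B would already be confined to them and the 60/35 split would not apply. Section 3.1 and Section 13.1 support upfront randomisation, but the conflict is real.

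**Conclusion.** The point holds as a cheap improvement, not as an error in the test. Failures shared by two identically treated, blinded arms dilute the A-versus-B comparison, and a comparison stratified by the Week 104 result had more power in every scenario tabulated.

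With Arm A at 0.35 overall, the loss is at most about 5 points when 90% pass Week 104 and about 11 when 80% pass. It is about 18 to 20 when 70% pass and Arm B retains 80 to 90%. It exceeds 20 to 30 only when about 60% pass and Arm B retains 85% or more. With 6/16 for Arm A among passers, it is about 3 to 15.

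These figures assume the same Week 104 pass rate in A and B, the blind holding to Week 104, and success requiring a pass at both visits. The A-versus-C primary analysis is unaffected.

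**What to change.** Keep the intent-to-treat A-versus-B test as a reported result. Beside it, pre-specify an A-versus-B Mantel-Haenszel test stratified by one defined status, passing the Week 104 challenge, with success as in 13.1 and 13.6 (both Week 104 and Week 117). The stratum that failed Week 104 has no successes and contributes nothing to the test.

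Give the risk difference within the stratum that passed. A pooled Mantel-Haenszel difference would average in the zero from the other stratum and dilute the estimate again. State that the result applies to subjects who reached the switch and relies on the blind holding to Week 104.

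Three places must be reconciled: the Week-117-only success definition in 13.4.2 with 13.1 and 13.6; the and/or in the Week 104 criteria; and the 1:1 randomisation in 8.3 with the upfront 2.4:1.4:1 randomisation.

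The cost is a few sentences and no new data. The A-versus-C primary stays as it is.

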13.4.4 Analyses of Secondary and Other Endpoint(s)/Outcome(s)

The following proportions will be estimated, with 95% exact binomial confidence intervals:

- Proportion in arm A who pass the DBPCFC week 130, 143, and 156 of peanut avoidance,
- Proportion, in arms A and B combined, who can successfully complete the build-up phase of peanut OIT to the highest dose (4,000 mg of peanut protein) with only mild (Objective, APPENDIX 4) symptoms,
- Proportion, in arms A and B combined, who can successfully undergo the build-up and maintenance phases of peanut OIT with only mild symptoms,
- Proportion, in arms A and B combined, defined as treatment failures at initial dose escalation or at 1000 mg protein,
- Proportions, in arms A and B separately, who are defined as desensitization failures at week 117 (or equivalent), 130, 143, and 156, and

• Proportion, in arm A who are defined as tolerance failures at week 117 (or equivalent), 130, 143, and 156.

Adverse events will be tabulated, using the safety sample.

13.4.5 Analyses of Exploratory Endpoint(s)/Outcome(s)

We will use blood samples and clinical outcome measurements from this study to identify specific features of the immune response that are associated with "clinical tolerance" at week 104, 117 (or equivalent), 130, 143, and 156. We will also determine special immune features associated with subjects who are desensitized at week 104, 117 (or equivalent), 130, 143, and 156. It will be important to compare any of the immune features to those of the placebo arm, treatment failures, tolerance failures, and desensitization failures. This exploratory objective may be examined prior to study closeout. In such a case, only the statisticians will have access to identity of study arm. Study arm, however, will not be a variable in the analysis prior to study closeout. Instead the outcome of interest will be clinical tolerance/desensitization across study arms and the interest will lie in correlating molecular features to the outcome.

A number of post-hoc analyses for predicting clinical outcomes will be completed looking at clinical and mechanistic variables.

13.4.6 Descriptive Analyses

Descriptive statistics (proportions for categorical variables, means and standard deviations for continuous variables) will be reported for all key participant variables, including baseline and demographic characteristics, use of medications, compliance, and study completion status.

13.5.1 Interim Analyses

N/A – There will be no interim analyses in this protocol.

Although no formal interim analyses are specified, we will examine one set of exploratory objectives prior to study closeout that do not involve our primary efficacy endpoint, nor do they reveal data by study arm. Specifically, the outcome of interest will be clinical tolerance/desensitization aggregated across study arms and the interest will lie in correlating molecular features to the outcome.

13.6. Statistical Hypotheses

For the primary comparison, the following will be tested:

- Null hypothesis: The success rate (where success is passing the DBPCFC at both 104 and 117 (or equivalent) weeks) is equal in arms A (active treatment followed by 3 months of avoidance) and C (placebo).
- Alternative hypothesis: The success rate differs between arms A and C.

As a secondary comparison, the following will be tested:

- Null hypothesis: The success rate is equal in arms A and B (active treatment followed by 3 months of 300mg peanut protein treatment).
- Alternative hypothesis: The success rate differs between arms A and B.

13.7. Sample Size Considerations

In the previous trial by Burks et al, 2013 the rate of success among subjects treated as in arm A was 0.35. Literature (Sampson, et al. 2013) suggests that the rate of success among subjects on placebo (as in arm C) is

0.05 or less. Using a binomial test of proportions with two-sided alpha level 0.05, the sample size of 60 subjects on arm A and 25 subjects on arm C yields 90% power to detect that difference (between rates of 0.35 and 0.05). According to the definition of the endpoint – passing the DBPCFC at both 104 and 117 (or equivalent) weeks – subjects who drop out of the study are included in the analysis (counted as failures). Therefore, the analysis will include all subjects randomized to arm A or arm C, and the sample size is not decreased due to drop-outs.

The following table displays the power for other possible success rates in the two arms.

		Arm C Population Success R	ate	
		0.025	0.05	0.075
Arm A	0.25	76%	59%	44%
Population	0.30	89%	77%	64%
Success	0.35	96%	90%	80%
Rate	0.40	99%	96%	91%
	0.45	100%	99%	97%

14. Identification and Access to Source Data

14.1. Source Data

Source documents and source data are considered to be the original documentation where subject information, visits consultations, assessments and other information are recorded. Documentation of source data is necessary for the reconstruction, evaluation and validation of clinical findings, observations and other activities during a clinical trial.

In this protocol, source data will be recorded onto paper CRFs at the time of collection. Skin test results will be recorded via adhesive tape transfer of the outline of any wheal(s) and/or erythema. Spirometry results will be recorded as printouts from the software package used to perform the testing.

14.2. Access to Source Data

The site investigator and site staff will make all source data available to the PPD Monitor, DAIT/NIAID, as well as to the FDA. Authorized representatives as noted above are bound to maintain the strict confidentiality of medical and research information that may be linked to identify individuals.

15.Protocol Deviations

15.1. Protocol Deviation Definitions

Protocol Deviation – The investigators and site staff will conduct the study in accordance to the protocol; no deviations from the protocol are permitted. Any change, divergence, or departure from the study design or procedures constitutes a protocol deviation. As a result of any deviation, corrective actions will be developed by the site, approved by the NIAID and then implemented promptly.

Major Protocol Deviation - A major protocol deviation is a deviation from the IRB approved protocol that may affect the subject's rights, safety, or well-being and/or the completeness, accuracy and reliability of the study data. In addition, major protocol deviations include willful or knowing breaches of human subject protection regulations, or policies, any action that is inconsistent with the NIH Human Research Protection Program's research, medical, and ethical principles, and a serious or continuing noncompliance with federal, state, local or institutional human subject protection

regulations, policies, or procedures. This also includes departures from GCPs and pharmacy handling of the investigational product and accountability.

Non-Major Protocol Deviation - A non-major protocol deviation is any change, divergence, or departure from the study design or procedures of a research protocol that does not have a major impact on the subject's rights, safety or well-being, or the completeness, accuracy and reliability of the study data.

15.2. Reporting and Managing Protocol Deviations

The study site principal investigator has the responsibility to identify, document and report protocol deviations as directed by the NIAID (**Appendix 3**). However, protocol deviations may also be identified during site monitoring visits conducted by the PPD monitor, or during other forms of study conduct review.

Deviations from the protocol will be reviewed by the NIAID project manager, on a case-by-case basis, to determine if the deviation meets major or non-major criteria. All protocol deviations and the reasons for such deviations must be noted on the appropriate CRF.

Protocol Deviation reports will be submitted by study site personnel in accordance with requirements from the local IRB, the FDA, and the NIAID. Action plans to prevent deviations going forward will be reviewed and approved by the NIAID Project Manager and Medical Monitor.

16.Ethical Considerations and Compliance with Good clinical Practice

16.1. Statement of Compliance

This clinical study will be conducted using good clinical practice (GCP), as delineated in *Guidance for Industry: E6 Good Clinical Practice Consolidated Guidance*, and according to the criteria specified in this study protocol. Before study initiation, the protocol and the informed consent documents will be reviewed and approved by the IRB. Any amendments to the protocol or to the consent materials will also be approved by the IRB before they are implemented.

16.2. Informed Consent Process

The consent process will provide information about the study to a prospective participant and will allow adequate time for review and discussion prior to his/her decision. The principal investigator or study physician listed on the FDA 1572 will review the consent and answer questions with the potential participant and the study physician must sign the consent form with the participant and document the informed consent process. For minors participating in this study, informed consent will be obtained from their parent(s) or legal guardian(s). Minors participating in this study will provide assent if they are capable. The prospective participant will be told that being in the trial is voluntary and that he or she may withdraw from the study at any time, for any reason. All participants (or their legally acceptable representative) will read, sign, and date a consent form before undergoing any study procedures. Consent materials will be presented in participants' primary language. A copy of the signed consent form will be given to the participant.

The consent process will be ongoing. The consent form will be revised when important new safety information is available, the protocol is amended, and/or new information becomes available that may affect participation in the study.

